## NON-INTERVENTIONAL POST-AUTHORIZATION STUDY PROTOCOL

---

Study Title	Multi-country, non-interventional, cohort study of the effectiveness, safety, adherence, and health-related quality of life in HIV-1 infected adult patients receiving Bictegravir/ Emtricitabine/Tenofovir alafenamide (B/F/TAF)
Protocol ID	GS-EU-380-4472
Protocol Version/Date:	Final: Version 5.0      21 Oct 2020
EU PAS Register No	EUPAS22185
Clinical Trials.gov Identifier	Not Applicable
Active substances	ATC Code: J05AR20, Antivirals for systemic use; antivirals for treatment of HIV infections, combinations. Bictegravir, Emtricitabine, Tenofovir Alafenamide
Medicinal Product	Bictegravir/ Emtricitabine/Tenofovir Alafenamide fixed dose combination
Product reference	EU/1/18/1289/001-002 (EU); 06.03.2019 - 2019/135 (Turkey)
Procedure number	Not Applicable
Research Question and Objectives	To assess the effectiveness and safety of B/F/TAF in treatment naive and treatment experienced HIV-1 infected adult patients, including adherence, resource utilization, quality of life, health status, and treatment satisfaction during its daily routine use.
Countries of study	As a minimum, the following countries are likely to be included: Germany, Netherlands, Ireland, United Kingdom, France, Italy, Spain, and Turkey.

PPD /  

## GLOSSARY OF ABBREVIATIONS AND DEFINITION OF TERMS

ABC	Abacavir
ADR	Adverse Drug Reaction
AE	Adverse Event
ART	Antiretroviral Therapy
ARV	antiretroviral
BfArM	The Federal Institute of Drugs and Medical Devices in Germany
BIC	Bictegravir
B/F/TAF	Bictegravir/ Emtricitabine/Tenofovir alafenamide
CD4	cluster determinant 4
CD8	cluster determinant 8
CDC	Centers for Disease Control and Prevention
CRF	Case Report Form
DTG	Dolutegravir
eCRF	Electronic Case Report Form
EDC	Electronic Data Capture
EMA	European Medicines Agency
FDC	Fixed Dose Combination
FTC; F	Emtricitabine
GLPS	Global Patient Safety
GPP	Good Pharmacoepidemiology Practices
GVP	Good Pharmacovigilance Practices
HIV	Human Immunodeficiency Virus
CCI	[REDACTED]
[REDACTED]	[REDACTED]
[REDACTED]	[REDACTED]
[REDACTED]	[REDACTED]
HMA	Heads of Medicines Agencies
HRQoL	Health Related Quality of Life
ICF	informed consent form
IEC	Independent Ethics Committee
INSTI	Integrase Strand-Transfer Inhibitor
MAH	Marketing Authorization Holder
MAR	missing at random
MCAR	missing completely at random
MICE	multiple imputation by chained equations
NRTI	Nucleoside Reverse Transcriptase Inhibitor
NtRTI	Nucleotide Reverse Transcriptase Inhibitor
PAS	Post-Authorization Study
PRO	patient reported outcome

PSMF	Pharmacovigilance System Master File
PVE	Pharmacovigilance and Epidemiology
Q1	first quartile
Q3	third quartile
QPPV	Qualified Person for Pharmacovigilance
RNA	ribonucleic acid
SADR	Serious Adverse Drug Reaction
SAE	Serious Adverse Event
SAP	Statistical Analysis Plan
SD	standard deviation
CCI	
SmPC	summary of product characteristics
SSR	Special Situation Report
TAF	tenofovir alafenamide (Vemlidy®)
TAFNES	Non-Interventional Real-Life Study of Effectiveness, Safety, Adherence, and Health-Related Quality of Life in Adult Patients receiving Elvitegravir/Cobicistat/Emtricitabine/Tenofovir alafenamide (E/C/F/TAF) or Emtricitabine/Tenofovir alafenamide (F/TAF) or Rilpivirine/Emtricitabine/Tenofovir alafenamide (R/F/TAF) for HIV-1 Infection in Germany
3TC	lamivudine
US, USA	United States, United States of America
VAS	visual analogue scale

## 2. PROTOCOL SYNOPSIS/ABSTRACT

**Gilead Sciences Europe Ltd**  
**[name]**  
**[name]**

---

**Study Title:** Multi-country, non-interventional, cohort study of the effectiveness, safety, adherence, and health-related quality of life in HIV-1 infected adult patients receiving Bictegravir/Emtricitabine/Tenofovir alafenamide (B/F/TAF)

**Rationale and Background:** Current treatment guidelines recommend that patients initiate antiretroviral therapy (ART) at time of diagnosis, leading to the requirement for lifelong treatment. Accordingly, there is a need for new HIV-1 therapies that improve the current standard of care so that lifelong ART is more effective, more tolerable, and safer for patients.

Bictegravir (BIC) is a novel unboosted integrase strand-transfer inhibitor (INSTI) with potent activity against HIV-1 integrase and an enhanced resistance profile. Gilead Sciences has co-formulated BIC with the nucleoside reverse transcriptase inhibitor (NRTI) emtricitabine (FTC; F) and the nucleotide reverse transcriptase inhibitor (NtRTI) tenofovir alafenamide (TAF) into a single tablet that is suitable for once-daily use. This B/F/TAF single tablet regimen may provide a potent, convenient, tolerable, and practical regimen for the life-time treatment of people living with HIV.

While large Phase 3 clinical trials are necessary to support the registration of new drugs, these studies are performed in highly selected patients under controlled conditions. Thus, data derived from observational cohorts that reflects a more heterogeneous patient population are important in helping physicians better understand the use of new drugs in real-life healthcare settings.

The aim of this non-interventional, multi-country, cohort study is to evaluate the effectiveness and safety of B/F/TAF in ART-naive and ART-experienced HIV-1 infected adult patients as well as adherence, resource utilization, quality of life, health status, and treatment satisfaction during its daily routine use.

**Research Questions  
and Objectives:**

This non-interventional cohort study will evaluate the effectiveness, safety, adherence, resource utilization and patients' health condition via patient-reported outcome (PRO) questionnaires, during treatment with B/F/TAF in routine clinical care.

The primary objective of this study is as follows:

- To evaluate HIV-1 RNA suppression, defined as HIV-1 RNA <50 copies/mL, at 12 months after initiating or switching to B/F/TAF

The secondary objectives of this study are as follows:

- To evaluate HIV-1 RNA suppression (<50 copies/mL) at Months 3, 6, and 24 for all patients after initiating or switching to B/F/TAF
- To evaluate changes in cluster determinant 4 (CD4) cell count and CD4/ cluster determinant 8 (CD8) ratio at Months 3, 6, 12, and 24 for all patients after initiating or switching to B/F/TAF
- To assess rates of adverse events (AEs) and serious adverse events (SAEs)
- To evaluate the long-term effectiveness and safety of B/F/TAF in an extension phase through Month 60 in a subgroup of patients recruited in Germany and France:

To evaluate HIV-1 RNA suppression (< 50 copies/mL) at Months 36, 48, and 60 after initiating or switching to B/F/TAF

To evaluate changes in CD4 cell count and CD4/CD8 ratio at Months 36, 48, and 60 after initiating or switching to B/F/TAF

CCI

[REDACTED]

CCI

The above parameters may be evaluated in various subgroups, e.g., ART-naive patients versus ART-experienced patients, by baseline viral load  $\geq$  or  $<$  100,000 copies/mL, age, presence of specific comorbidities, gender, as well as comparing between participating countries.

**Study Design:** Prospective, non-interventional cohort study. Patient enrollment and data will be collected using an electronic case report form (eCRF) by the participating sites. Each enrolled patient will be followed-up for 24 months (or 60 months for those patients entering the extension phase in Germany and France).

**Population:** The study population will be comprised of ART-naive and ART-experienced HIV-1 infected adults aged  $\geq$  18 years initiating treatment with B/F/TAF in routine clinical care.

As a minimum, the following countries are likely to be included: Germany, Netherlands, United Kingdom, Ireland, France, Italy, Spain, and Turkey.

**Variables:** Baseline and follow-up variables are specified in section 7.3 and include amongst others: demographics, clinical characteristics (i.e., comorbidities), laboratory measurements, medications (i.e., prior antiretroviral [ARV] and concomitant medications), adherence and PROs.

**Data Sources:** Electronic data capture (EDC) at each participating site will collect study variables gathered from routine standard care.

**Study Size:** At least 1500 patients starting treatment with B/F/TAF (to include both ART naive and ART experienced patients) are planned to be enrolled into the study.

A sample size of 1500 patients will be appropriate to detect a proportion of HIV RNA suppression ( $<$  50 copies/mL) of at least 90% with a power of 80% (Score z test: target proportion 90%, smallest detectable proportion 92.10%).

Additionally, assuming there are 30% of patients over age 50 years, then with 1050 patients  $<$  50 years and 450 patients 50 years or older, there is more than 90% power to detect a difference in HIV RNA response rate between the age groups of at least 7%, assuming

a 90% response rate in older patient (versus 83% in younger patients) and a two-sided alpha of 0.05 and a continuity corrected test of two proportions.

With a target of at least 200 patients per country, there is 80% power to determine a 7% difference in HIV RNA response rates between any country and the remaining countries, assuming a 90% response rate in the overall countries. In addition, assuming a 90% response rate in one country with 200 patients, there is more than 80% power to determine an 11% difference in HIV RNA response rates compared to any country including the same sample size.

The study will not have strict enrollment goals for specific strata of patient types. However, the protocol team will monitor enrollment into specific strata of interest (eg, age > 50 years, treatment naive) and may close enrollment to a stratum in order to preserve statistical power to evaluate subgroups of interest.

Patients recruited in Germany, France, and Canada (protocol ID: GS-CA-380-4574) will be included in the extension phase HIV RNA analysis at Month 60. From the existing cohort of patients, a subsample of 400 patients will be appropriate to detect a proportion of HIV RNA suppression of at least 70% with a power of 80% (Score z test: target proportion 70%, smallest detectable proportion 76.4%). A cumulative drop-out rate of 35% at Month 60 was applied to derive the projected Month 60 sample size.

#### **Data Analysis:**

For categorical variables, numbers and percentages of patients will be reported including the according 95% confidence intervals.

For continuous variables, mean, SD, minimum, first and third quartile (Q1, Q3), median, maximum and 95% confidence intervals will be calculated, together with the total number of observations and the number of missing values.

Descriptive statistics will summarize demographics and baseline characteristics.

The questionnaires scores will be calculated according to the algorithms elaborated for these questionnaires.

Visit windows will be defined only in the statistical analysis plan to group data in order to generate descriptive statistics across time to assess potential trends in PRO questionnaires, safety data, or CD4 cell count. P-values and confidence intervals (95% two-sided) will be calculated when considered relevant.

Multivariate logistic regression models will be used to model binary outcome variables (HIV-1 RNA suppression, categorical CD4 cell count, i.e., > 500, adherence and persistence of B/F/TAF).

Multivariate Poisson regression models will be used to model questionnaires scores (CCI [REDACTED]) and rates of AEs and SAEs.

Multivariate analyses will also be conducted to compare ART-naive and ART-experienced groups. Longitudinal analysis will be performed using mixed models.

Further details of the data analysis will be provided in the Statistical Analysis Plan.

Milestones:	EU PAS Registration	Q1 2018
	Start of data collection:	Q2 2018
	End of data collection:	Q3 2024
	Final report:	Q3 2025

---

This study will be conducted in accordance with the guidelines of Good Pharmacoepidemiology Practices (GPP) and Heads of Medicines Agencies (HMA) Good Pharmacovigilance Practices (GVP) including archiving of essential documents.

### 3. AMENDMENTS AND UPDATES

Amendment or Update Number	Date	Section of Study Protocol	Amendment or Update	Reason
1	14 June 2018	Protocol title page and section 11	Change from post-authorization safety study (PASS) to post-authorization study (PAS)	The Federal Institute for Drugs and Medical Devices (BfArM) advice
2	26 March 2019	Cover pages, responsible parties, exclusion criteria, milestones  Safety & PROs	Product Reference New Marketing Authorization Holder (MAH)  Updated details for QPPV  Deletion of Sponsor Addition of United Kingdom to the study  Remove observational studies from exclusion criteria Start of data collection  Clarification of safety terms  Clarification of administration	Changes needed due to Brexit  Sponsor Not Applicable Addition of United Kingdom  Patients are allowed to take part in other observational research  Updated timelines Clarification Clarification

Amendment or Update Number	Date	Section of Study Protocol	Amendment or Update	Reason
3	19 May 2020	Responsible parties  Population  Milestones   Investigator Reporting Requirements to Gilead	Team changes and administrative update for correctness  Addition of Turkey  End of data collection extended Update in the site reporting requirements for non-serious Adverse Events	Addition of Turkey as new country  Non-serious events not deemed to be related to study treatment will be retained solely in the Clinical Database and not also captured in the Safety Database  Extension of data collection period
4	21 Oct 2020	Study Design          Milestones	Additional patient follow-up included in study design from 24 to 60 months for patients in Germany and France  CCI [REDACTED]  End of data collection extended from Q4 2023 to Q3 2024  Final report changed from Q4 2024 to Q3 2025	Extended the duration of follow-up to allow for collection of long-term effectiveness and safety data

## **Protocol Modifications**

Protocol modifications may only be made by Gilead.

#### 4. MILESTONES

Milestone	Planned Date
EU PAS Registration	Q1 2018
Start of data collection	Q2 2018
End of data collection	Q3 2024
Final report of study results	Q3 2025

## 5. RATIONALE AND BACKGROUND

Current treatment guidelines recommend that patients initiate antiretroviral treatment (ART) earlier, thereby requiring lifelong treatment, potentially for 50 years or more. Accordingly, there is a need for new HIV-1 therapies that improve the current standard of care so that lifelong ART is more effective, more tolerable, and safer for patients.

Bictegravir (BIC) is a novel unboosted integrase strand-transfer inhibitor (INSTI) with potent activity against HIV-1 integrase and an enhanced resistance profile {[Tsiang 2016](#)}. Gilead Sciences has coformulated BIC with the nucleoside reverse transcriptase inhibitor (NRTI) emtricitabine (FTC; F) and the nucleotide reverse transcriptase inhibitor (NtRTI) tenofovir alafenamide (TAF) into a single tablet that is suitable for once-daily use. This B/F/TAF fixed-dose combination (FDC) may provide a potent, convenient, tolerable, and practical regimen for the life-time treatment of people living with HIV.

In a phase 2, double-blind, randomized controlled trial, ART-naïve patients were randomly assigned to receive BIC (as the single agent) or dolutegravir (DTG), both with F/TAF. At 48 weeks, 97% of the BIC treated patients and 91% of the DTG treated patients achieved HIV-1 RNA of < 50 copies/mL, with no treatment emergent resistance in either arm {[Sax 2017a](#)}.

Based on the results of the phase 2 study, two large, ongoing, phase 3, double-blind, randomized-controlled trials in ART-naïve patients compared B/F/TAF FDC to either coformulated abacavir, DTG and lamivudine (ABC/DTG/3TC) (GS-US-380-1489) or DTG with F/TAF (GS-US-380-1490). Both studies demonstrated that virological suppression with B/F/TAF was non-inferior to the DTG-based regimen in ART-naïve patients. At 48 weeks, 92% on B/F/TAF versus 93% on ABC/DTG/3TC {[Gallant 2017](#)} and 89% on B/F/TAF versus 93% on DTG plus F/TAF {[Sax 2017b](#)} achieved HIV-1 RNA < 50 copies/mL. There was no treatment emergent resistance to any component of either regimen. The FDC of B/F/TAF was safe and well tolerated compared with the DTG-based regimens.

Two further ongoing phase 3 studies are evaluating B/F/TAF in virologically suppressed patients switching from an existing antiretroviral regimen containing either DTG (GS-US-380-1844) or a boosted protease inhibitor (GS-US-380-1878). In study GS-US-380-1878, switching to B/F/TAF was non-inferior to continuing a boosted darunavir- or atazanavir-based regimen with 92% versus 89% of patients achieving HIV-1 RNA < 50 copies/mL at 48 weeks and no patients treated with B/F/TAF developed resistance {[Daar 2017](#)}.

While large phase 3 clinical trials are fundamental to supporting the registration of new drugs, these studies are performed in highly selected patients under well controlled conditions. The results of such trials may be limited in terms of their generalizability to the wider HIV-infected population. Thus, there is a need for data derived from more heterogeneous patient populations, such as in observational cohorts, in order to help physicians gain a better understanding of the use of new drugs in real-life healthcare settings.

The aim of this non-interventional, multi-country, cohort study is to evaluate the effectiveness and safety of B/F/TAF in ART-naïve and ART-experienced HIV-1 infected adult patients as well as adherence, resource utilization, quality of life, health status, and treatment satisfaction during routine clinical practice.

## 6. RESEARCH QUESTIONS AND OBJECTIVES

This non-interventional cohort study will evaluate the effectiveness, safety, adherence, resource utilization and PROs of B/F/TAF use in routine clinical care.

The primary objective of this study is:

- To evaluate HIV-1 RNA suppression, defined as HIV-1 RNA < 50 copies/mL, at 12 months after initiating or switching to B/F/TAF

The secondary objectives of this study are:

- To evaluate HIV-1 RNA suppression (<50 copies/mL) at Months 3, 6, and 24 for all patients after initiating or switching to B/F/TAF
- To evaluate changes in cluster determinant 4 (CD4) cell count and CD4/cluster determinant 8 (CD8) ratio at Months 3, 6, 12, and 24 for all patients after initiating or switching to B/F/TAF
- To assess rates of adverse events (AEs) and serious adverse events (SAEs)
- To evaluate the long-term effectiveness and safety of B/F/TAF in an extension phase through Month 60 in a subgroup of patients recruited in Germany and France:

To evaluate HIV-1 RNA suppression (< 50 copies/mL) at Months 36, 48, and 60 after initiating or switching to B/F/TAF

To evaluate changes in CD4 cell count and CD4/CD8 ratio at Months 36, 48, and 60 after initiating or switching to B/F/TAF

CCI [REDACTED]

- [REDACTED]
- [REDACTED]
- [REDACTED]
- [REDACTED]
- [REDACTED]

CCU [REDACTED]

[REDACTED]

[REDACTED]

The above parameters may be evaluated in various subgroups, e.g., ART-naive patients versus ART-experienced patients, by baseline viral load  $\geq$  or  $<$  100,000 copies/mL, age, presence of specific comorbidities, gender, as well as comparing between participating countries.

## **7. RESEARCH METHODS**

### **7.1. Study Design**

This non-interventional study will be a prospective cohort comprised of HIV-1 infected adults who initiate B/F/TAF therapy in accordance with the approved summary of product characteristics (SmPC).

Patients can be enrolled in this study after the physician has independently decided to treat a specific patient with B/F/TAF and after patient's informed consent form (ICF) is obtained. Although the study will not define which therapy a patient will receive, only patients starting or switching to B/F/TAF will be enrolled.

Patient data will be collected prospectively according to clinical practice from initial enrollment into the study (Day 1/baseline) and thereafter (follow-up period) until study completion at Month 24 (or Month 60 for those patients entering the extension phase in Germany and France), lost to follow-up, withdrawal of consent, or death, whichever occurs sooner. Day 1/Baseline will be defined as the time at which patients either start (ART-naive) or switch to (ART-experienced) B/F/TAF.

#### **7.1.1. Early Study Drug Discontinuation**

In case of B/F/TAF discontinuation, the date of discontinuation, reasons for discontinuation (eg, patient choice, adverse reaction, lack of efficacy) and patients' new ART will be collected. The patient will remain in the study and will be followed-up with the new ART until premature end of documentation (e.g., due to lost to follow-up) or until reaching the defined end of the study (24 months after enrollment). If the patient has subsequent changes in therapy, all ARV changes will be recorded until the patient completes the study.

For the extension phase of the study, applicable for patients in Germany and France: In case of B/F/TAF discontinuation in the extension phase, patients must be discontinued from the study with no further follow-up data being collected.

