### 7.3. Variables

	On-Treatment Period				B/F/TAF Discontinuation l
	Baseline/Day 1	3 Months	6, 12, 24 Months	36, 48, 60 Months*	
Informed consent	X			X**	
Demographics	X				
Weight	X		X	X	X
Date of HIV diagnosis	X				
CDC classification a	X				
New AIDS defining events		X	X	X	X
Co morbidities	X				
ART History	X				
Concomitant medications	X	X	X	X	X
Plasma HIV 1 RNA	X	X	X	X	X
CD4 cell count	X	X	X	X	X
CD4/CD8 ratio	X	X	X	X	X
Chemistry profile b	X		X	X	X
Metabolic assessments c	X		X	X	X
Urinalysis d	X		X	X	X
Reasons for ART initiation or switch to B/F/TAF	X				
AEs and SAEs		X	X	X	X
Resistance status	X		X	X	
CCI					
CCI					
CCI					
CCI					
Health Utilization Assessment			X	X	
CCI					

- a Selik RM, et al. Morbidity and Mortality Weekly Report (MMWR). Revised Surveillance Case Definition for HIV Infection United States 2014. Centers for Disease Control and Prevention, 2014.  
 CDC: Centers for Disease Control and Prevention
- b Chemistry profile: AST, ALT, Total/direct bilirubin, albumin, serum glucose, serum phosphate, serum creatinine.
- c Metabolic assessments: Lipid panel (Total cholesterol, HDL, LDL, triglycerides).
- d To include dipstick test (glucose, leukocytes, protein) and urine albumin/creatinine ratio (UACR), urine protein/creatinine ratio (UPCR).

l The evaluations should be done at the time of B/F/TAF discontinuation visit. After the B/F/TAF discontinuation visit, the subject should follow the same schedule of clinical routine evaluations, but only record data listed in this column until study completion.

Note: Patients who discontinue B/F/TAF in the extension phase are required to discontinue the study with no further follow up.

\* Only applicable for patients consenting to the extended patient follow up in Germany and France

\*\* Patients who are willing to participate in the extension phase could either re-consent onsite during 24M visit or remotely, in case the 24M visit was completed prior receiving the protocol amendment approval by country regulatory bodies.

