### 9.1. Investigator Instructions for Collecting and Reporting Selected Safety Information to Gilead

The following safety information is required to be collected for this study from the time of the patient's consent to participate in the study (ie, signing informed consent) until study completion at Month 60, lost to follow-up, withdrawal of consent, or death, whichever occurs sooner - this applies even if patients prematurely discontinue B/F/TAF.

- All fatal events (regardless of causality)
- All SAEs (serious adverse events) (regardless of causality)
- All AEs (non-serious adverse events) (regardless of causality)
- Special Situation Reports (SSRs)

**Note: non-serious AEs deemed not to be related to study treatment are required to be collected within the eCRF but not reported to Gilead Global Patient Safety (GLPS) (formerly Pharmacovigilance and Epidemiology [PVE]).**

Timelines for reporting to Gilead are as follows:

- Within 3 calendar days of investigator's knowledge of all fatal events (regardless of causality) and all SAEs
- Within 30 calendar days of investigator's knowledge of non-serious AEs deemed to be related to study treatment
- Within 30 calendar days of investigator's knowledge for SSRs

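### Sections 7.1.1 and 7.3 end all data collection when B/F/TAF is stopped in the extension, while Section 9.1 requires safety data to Month 60 after a stop; outcomes after the stop are lost

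*Protocol*

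**What the plan says.** **Main phase, to Month 24 (Protocol Section 7.1.1).** After a stop, the date, the reason and the new ART are recorded. Patient choice, adverse reaction and lack of efficacy are given as example reasons. Follow-up then continues: "The patient will remain in the study and will be followed-up with the new ART until premature end of documentation" or the 24-month end of study.

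**Extension, Germany and France (same section).** The rule reverses: "In case of B/F/TAF discontinuation in the extension phase, patients must be discontinued from the study with no further follow-up data being collected". The note under the Section 7.3 table agrees: "Patients who discontinue B/F/TAF in the extension phase are required to discontinue the study with no further follow up".

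**Discontinuation visit (Section 7.3).** A footnote says "The evaluations should be done at the time of B/F/TAF discontinuation visit". The column includes HIV-1 RNA, CD4 count, CD4/CD8 ratio and AEs/SAEs. Resistance status has no mark there. For visits after the stop, sites follow the routine schedule "but only record data listed in this column until study completion".

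**Safety reporting (Section 9.1).** Deaths, SAEs, non-serious AEs and special situation reports are collected from consent "until study completion at Month 60, lost to follow-up, withdrawal of consent, or death", whichever comes first, and "this applies even if patients prematurely discontinue B/F/TAF". No exception is made for the extension, and Month 24 is not mentioned.

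**End of follow-up (Section 7.1).** Month 24, or Month 60 for extension patients, loss to follow-up, withdrawal of consent, or death. Stopping B/F/TAF is not on the list.

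**Objectives (Section 6).** The extension is to assess long-term effectiveness and safety in a subgroup from Germany and France, with suppression "at Months 36, 48, and 60 after initiating or switching to B/F/TAF".

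**The concern.** Two instructions to sites contradict each other on whether deaths and SAEs are collected. An analysis plan cannot settle this, because it does not tell sites what to record.

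If Sections 7.1.1 and 7.3 are followed, a patient who stops in the extension contributes nothing after the discontinuation visit. Two of the three example reasons for stopping are tied to the outcomes under study, so the missing values are probably informative. Suppression on a later regimen, later CD4 values and safety after the stop would be unobserved for Months 36 to 60, whereas they are observed up to Month 24. Values that were never collected cannot be recovered at analysis.

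**Working it through.** **1. The passages side by side.** Take an SAE or death after a patient stops B/F/TAF at Month 40 (an invented case).

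| Section | Is the event collected? |
|---|---|
| 7.1.1, extension paragraph | No; the patient has left the study |
| 7.3, note | No |
| 7.1 | Yes, by omission: stopping does not end follow-up |
| 9.1 | Yes, explicitly; reported within 3 calendar days |

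Section 7.1.1 cannot simply be read as a specific rule overriding a general one, because Section 9.1 also addresses patients who have stopped.

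For a patient outside the extension, Section 7.1 ends collection at Month 24 and Section 9.1 at Month 60. These differ too.

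**2. What is kept and what is lost.** Kept: data up to the stop, the date of and reason for stopping, and one set of evaluations at the discontinuation visit. Lost: everything later.

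**3. The plan's own extension figure (Section 7.5).** Inputs: n = 400, p0 = 0.70, p1 = 0.764, score z test. Two-sided alpha 0.05 is assumed; the protocol states it only for the age comparison.

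- Standard error under p0: sqrt(0.70 × 0.30 / 400) = 0.0229; times 1.96 = 0.0449.
- Standard error under p1: sqrt(0.764 × 0.236 / 400) = 0.0212.
- Power = Φ((0.064 − 0.0449) / 0.0212) = 81.6%, against the stated 80%.

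The figure reproduces, and the present point makes no sample-size figure wrong. It supplies a yardstick: the analysis is sized for a difference of 6.4 points.

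**4. Size of the possible overstatement.** Compare an estimate from patients with on-drug values with the figure for all extension entrants, with no other losses:

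overstatement = share stopping × (suppression on drug − suppression among stoppers)

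Assumed, as the protocol gives none of these: 5-15% stop, 60-90% of stoppers are suppressed at the time point, 97% of those on drug are suppressed.

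- Low end: 0.05 × (0.97 − 0.90) = 0.0035, or 0.4 points.
- High end: 0.15 × (0.97 − 0.60) = 0.0555, or 5.6 points.

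If stoppers are instead counted as not suppressed on B/F/TAF, the gap from the on-drug figure is 0.05 × 0.97 = 4.9 to 0.15 × 0.97 = 14.6 points. That is a difference between two definitions, both calculable from data the protocol already collects, and not a bias.

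**5. A wider illustration.** Section 7.5 allows 35% cumulative drop-out at Month 60, not split by reason. Suppose half of it (17.5%) were stoppers in the extension, other losses resembled those observed, and 95% of those observed were suppressed. The overstatement would be 0.175 × (0.95 − 0.80) = 2.6 points if 80% of stoppers were suppressed, and 0.175 × (0.95 − 0.50) = 7.9 points if 50% were. The split and the suppression rates are again assumed.

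**The case against.** Following long-term users only while they take the drug is a defensible, limited design. The extension rule is stated openly in two places. A reader might infer more from it than the documents support:

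- **That the population changes silently under identical wording.** The secondary suppression objective for Months 3, 6 and 24 and the CD4 objective for Months 3 to 24 refer to all patients. The extension objectives name a country subgroup. Still, nothing in the objectives restricts them to patients on drug.
- **That the events behind a stop go unrecorded, or that AE rates are biased down.** The discontinuation visit records AEs and SAEs, and the reason for stopping is collected. A rate over on-drug time is not biased merely because later time is absent. What is missing is safety after the stop.
- **That Month 36-60 suppression must be an on-drug figure.** The protocol does not fix the denominator, and an analysis plan not shown here could count stoppers as not suppressed using the recorded stop date. The overstatement is therefore conditional.
- **That emergent resistance is underestimated.** The blank cell is a scheduling gap: a routine genotype at or after the stop has no scheduled entry. No visible objective estimates emergent resistance, though some objectives are redacted.
- **That a repair would make Months 3 to 60 one series.** Extension patients are a consenting subgroup, and the extension HIV RNA analysis includes patients from a Canadian protocol, so populations differ anyway.

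These points narrow the concern. They do not remove the contradiction, or the fact that data after the stop are never collected.

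**Conclusion.** The point holds in limited form. The conflict between Section 9.1 and Sections 7.1.1 and 7.3 is explicit, and it concerns the collection of deaths and SAEs. Section 7.1 sides with 9.1 by omission. The Month 60 limit in Section 9.1 is also wrong for patients outside the extension.

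If the extension rule stands, outcomes after the stop are unobserved, probably informatively. An estimate based only on patients with Month 36-60 values would then tend to overstate suppression among extension entrants. The illustrative range of 0.4 to 5.6 points runs from negligible to nearly the 6.4-point detectable difference, and rests wholly on the assumptions in step 4. The direction also depends on stoppers being less often suppressed than patients on drug, which is plausible but not documented.

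**What to change.** 1. **Reconcile Sections 7.1, 7.1.1, the 7.3 note and 9.1**, with Month 24 or Month 60 stated by phase. Preferably apply the main-phase recording rule to the extension, so that routine-care HIV RNA, CD4, AEs, SAEs and deaths are still recorded to Month 60 after a stop.
2. **Report Month 36, 48 and 60 suppression among all extension entrants**, with stoppers counted as not suppressed on B/F/TAF, beside the on-drug figure. The stop date already collected allows this. If data after the stop are not collected, label the extension results as on-treatment and state the limitation.
3. **Optionally, add resistance status to the discontinuation column**, recorded only where a routine test exists.

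Cost: a short protocol amendment, an eCRF edit for Germany and France, and some extra entry from routine records. Ethics submission (Section 8.2) and an updated consent (Section 8.3) may be needed, since patients would be followed beyond what is now the end of their participation. The recording rule should be checked against the Canadian protocol, which is not available here, so that the pooled analysis does not mix two rules. No visits or tests are added, and patient care does not change.
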